Nivolumab (Opdivo®; Bristol Myers Squibb [BMS]) is a fully human immunoglobulin G4 monoclonal antibody that binds to the PD-1 receptor, and which is used in patients with EC/GEJC as adjuvant therapy. PD-1 is an inhibitory receptor expressed on activated T cells that can negatively regulate T cell-mediated immune responses and promotes tumor development; by interacting with PD-1, nivolumab blocks PD-1 interaction with the ligands PD-L1 and PD-L2. This enables the release of PD-1 pathway-mediated inhibition of T cell immune response, including the anti-tumor immune response, thereby reducing tumor growth, and promoting tumor rejection.

The efficacy and safety of nivolumab in patients with resectable, locally advanced EC or GEJC has been demonstrated in CheckMate 577 (NCT02743494), a global, randomized, double-blind, placebo-controlled phase III trial that evaluated nivolumab as adjuvant treatment after neoadjuvant chemoradiotherapy and surgery. The trial population consisted of adult patients with resected (R0) stage II or III EC or GEJC who had received neoadjuvant chemoradiotherapy and had residual pathological disease. A total of 794 patients were randomly assigned at a ratio of 2:1 to receive nivolumab (532 patients) or placebo (262 patients, including two patients who did not receive the placebo). Patients were administered nivolumab at a dose of 240 mg every two weeks for 16 weeks, followed by nivolumab at a dose of 480 mg every four weeks or matching placebo. The trial intervention lasted for a maximum duration of a year. The primary efficacy endpoint was disease-free survival (DFS), defined as the time between randomization and the first recurrence (local, regional, or distant from the primary resected site) or death, from any causes, as assessed by the investigator prior to subsequent anti-cancer therapy. The median follow-up duration was 24.4 months at primary completion interim analysis.

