## 3.5 Definitions of Study Variables

#### 3.5.1 Outcome Variables

### 3.5.1.1 Clinical Outcomes

**Table 1** presents the definitions of the clinical outcome variables and **Table 2** presents definitions of clinical primary and secondary effectiveness outcomes that will be continuously evaluated as part of the study in all nivolumab patients and in patients that receive subsequent treatment(s) following nivolumab treatment.

Outcomes	Type of variables	Definition
Disease progression	Categorical	Disease progression will be evaluated at each available tumor assessment, which is collected either at first assessment after initial treatment' or during follow-up:
		Investigator assessed:
		
 
Disease progression = Yes, if best therapy tumor response = disease progression
 

		
 
Disease progression = No, if best therapy tumor response = complete/ near complete response, tumor shrinkage or mixed response
 

		• Per RECIST  :
		
 
Disease progression = Yes, if best therapy tumor response = PD
 

		
 
Disease progression = No, if best therapy tumor response=CR, PR, or SD
 

Recurrence	Categorical	Recurrence is defined as the detection of relapse of neoplastic disease during follow-up after nivolumab treatment initiation as assessed by the investigator
Type of recurrence (local/regional, metastatic)	Categorical	• Local recurrence is defined as a cancer that after treatment reappears at the primary site, i.e., at the site where it originated.
		• Regional recurrence is defined as cancer that reappears after treatment in the lymph nodes or tissues near the primary site.
		• Metastatic (distant) recurrence is defined as cancer that spreads (metastasizes) after treatment to distant organs or tissues such as the brain, kidneys, lungs, liver, or bone marrow.

Table 1. Clinical Outcomes Definition

Abbreviations: CR=Complete Response; PD=Progressive Disease; PR=Partial Response; SD=Stable Disease

Table 2: Primary and Secondary	Effectiveness	Outcomes Definition
---------------------------------------	---------------	----------------------------

Outcomes Type of variables	Definition
----------------------------	------------

Effectiveness outcomes in pati	ients initiating adju	uvant nivolumab treatment

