DFS	Time-to-event	Time between initiation of nivolumab treatment and the first date of recurrence (local, regional, or distant from the primary resected site) or death from any causes, whichever occurs first, as assessed by the investigator prior to subsequent anti-cancer therapy.
DFS rates	Continuous	DFS rates are defined as the probability that a patient is alive and presents no signs of recurrence at specific time points, following adjuvant nivolumab initiation.
08	Time-to-event	Time between initiation of nivolumab treatment until date of death due to any cause. Patients who are alive at last visit will be censored on date last known to be alive.
OS rates	Continuous	OS rates are defined as the probability that a patient is alive at specific time points, following adjuvant nivolumab initiation.
DMFS	Time-to-event	Time between initiation of nivolumab treatment and date of appearance of distant metastasis or death from any causes, whichever occurs first, as assessed by the investigator prior to subsequent anti-cancer therapy.
DMFS rates	Continuous	DFS rates are defined as the probability that a patient is alive and presents no signs of metastasis at specific time points, following adjuvant nivolumab initiation.
Time to recurrence	Continuous	Time between initiation of nivolumab treatment and the first date of recurrence.
Recurrence rates	Categorical	Recurrence rates are defined as disease recurrence (i.e., local/regional, metastatic) at specific time points, following adjuvant nivolumab initiation.
PRS	Time-to-event	PRS is defined as the interval from the date of any recurrence to the date of death from any cause. Patients who are alive at last visit will be censored on date last known to be alive.
Effectiveness outcomes in pati discontinuation:	ients that receive s	ubsequent treatment(s) following adjuvant nivolumab
OS of subsequent treatment	Time-to-event	Time between initiation of subsequent treatment until date of death due to any cause. Patients who are alive at last visit will be censored on date last known to be alive.
OS rates of subsequent treatment	Continuous	OS rates are defined as the probability that a patient is alive at specific time points, following subsequent treatment initiation.

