EC/GEJC stage at initiation	EC/GEJC Stage (i.e., II or III) and staging using TNM system at nivolumab treatment initiation	
Indication for nivolumab	Treatment indication	Day 0
Start date of nivolumab treatment	Date of nivolumab initiation	Day 0
Time from surgery to nivolumab initiation	Time from date of surgery to treatment nivolumab initiation	
Dosing	Dosing (i.e., frequency, dose, and number of administered doses), dose modifications (reasons for dose/frequency changes, interruption, and discontinuation)	All visits 
Other treatment(s)	-	
Concomitant type of treatment or therapies and details	Type of treatment or therapies receive in parallel of nivolumab treatment and details (e.g., medications, radiotherapy, chemotherapy, systemic therapy, or surgical treatment)	
Systemic treatment details, if applicable	
 
Type (Immunotherapy, targeted therapy, other)
 
Drug names
 
Dosage
 
Number of received administrations
 
Start date, end date
 
	All visits 
At completion/discontinuation of nivol	umab treatment	
End date of nivolumab treatment	Date of nivolumab treatment completion/discontinuation	
Permanent discontinuation of nivolumab	Permanent discontinuation is defined as 3 missed infusions. If nivolumab is restarted after 3 missed infusions, it should be considered as a new line of therapy (LOT).	
Temporary discontinuation	Temporary discontinuation is defined as 1 or 2 skipped infusions.	
Reason(s) for discontinuation	Reasons: death, disease progression, study drug related toxicity, non-study drug related toxicity, patient request, pregnancy, lost to follow-up, other	
Time-to-treatment discontinuation	Time from date of nivolumab treatment initiation to date of last infusion + 2 or 4 (if administered every 4 weeks) weeks (first 'missed' infusion), or the date of failure from a competing risk (e.g., death)	All visits 
Subsequent treatment after nivolumab discontinuation	
 
Yes/No
 
Type of treatment and details
 
Start date, end date
 
	
TTNT	
 
Start date, end date of nivolumab treatment
 
Start date, end date of subsequent treatment(s)
 
	
Modifications in relation to the management of AEs	Any changes in nivolumab treatment related to the management of AEs	
Treatment outcomes		
Disease stage after nivolumab treatment	EC/GEJC stage (i.e., II or III) and stage using TNM system	

Variables	Definition	Timing

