Recurrence	
 
Yes/No
 
Date of recurrence
 
Type of recurrence (i.e., local, regional, distant)
 
	
Disease progression	
 
Yes/No (as assessed by investigator or RECIST criteria)
 
Date of disease progression
 
	
Medical imaging test to assess treatment outcomesMedical imaging test used to assess recurrence of progression (e.g., computed tomography (CT) / r resonance imaging (MRI), Conventional X-ray, I details including method of assessment (i.e., by I or as assessed by the treating physician) and date assessment		All visits 
Death	

Yes/No

Date of death

Cause of death

	

 Data will be collected at visits Day 0, and Months 3, 6, 9, 12, 18, 24, 30, 36, and 42.

Abbreviations: AEs = adverse events; CT = computed tomography; EC = esophageal cancer; GEJC = gastroesophageal junction cancer; MRI = magnetic resonance imaging; PET = positron emission tomography; RECIST= Response evaluation criteria in solid tumors; TNM=Tumor Node Metastasis

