## 4.1.1.4 Subgroup Analyses

To meet the secondary and exploratory objectives, study outcomes will be summarized by subgroups of interest, depending on relevance, data availability and sample size including but not limited to:

- Patient and clinical characteristics:
  - o Country (US, Germany)
  - Sex (Male vs. female)
  - Age group ( $\leq 65$  vs. > 65)
  - o Race
  - Resection status (R0 vs R1)
  - Disease stage
  - o ECOG
  - Tumor location

- o Histology
- Pathologic lymph node status (ypN0 vs.  $\geq$  ypN1)
- Pathologic tumor status (ypT0 vs.  $\geq$  ypT1)
- Tumor cell PD-L1 expression
- Type of recurrence (local/regional vs. distant)

Furthermore, subgroup analyses (if sample size allows) will be performed according to Checkmate 577-like patient population vs. non-Checkmate 577 like patient population, using the key inclusion/exclusion criteria from the Checkmate-577 trial to determine the subgroups. This subgroup analysis will be performed to establish nivolumab safety and effectiveness in these two patient populations. If outcomes are similar between the two patient populations, this would support the use of nivolumab in almost all patients with EC and or GEJC.

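### The DFS event names recurrence or death but not the separately recorded disease progression, so regrowth after an R1 resection may go uncounted

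*Protocol*

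**What the plan says.** **The endpoint.** Section 3.5.1.1, Table 2, runs DFS from nivolumab initiation to "the first date of recurrence (local, regional, or distant from the primary resected site) or death from any causes, whichever occurs first". The judgement is the investigator's and is made before any subsequent anti-cancer therapy. The rate version agrees: "DFS rates are defined as the probability that a patient is alive and presents no signs of recurrence at specific time points". Neither definition mentions progression.

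**Recurrence and progression.** Table 1 defines recurrence in general terms, as relapse of the cancer found by the investigator after nivolumab has started. The local subtype is worded more narrowly: "Local recurrence is defined as a cancer that after treatment reappears at the primary site". Table 1 also defines disease progression, to be evaluated at every available tumour assessment. The introduction to Tables 1 and 2 covers all nivolumab patients as well as those on later treatment. Table 3 (section 3.5.1.2) lists recurrence and progression as two items, each with its own date. The progression item reads "Yes/No (as assessed by investigator or RECIST criteria").

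**Reasons for stopping nivolumab.** Table 3 gives "Reasons: death, disease progression, study drug related toxicity, non-study drug related toxicity" and further options, ending with an open category. Recurrence is not among them.

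**Who is enrolled.** Inclusion criterion 3 (section 3.3.1) asks for resected stage II/III disease, with no condition on margins. Table 3 records R0 or R1, Table 4 allows involved margins, and section 4.1.1.4 plans a subgroup by "Resection status (R0 vs R1"). Section 1.1 describes the CheckMate 577 population as "adult patients with resected (R0) stage II or III EC or GEJC" and its DFS event as "the first recurrence (local, regional, or distant from the primary resected site) or death, from any causes, as assessed by the investigator".

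**The concern.** After an R0 resection with clear margins, any later tumour is naturally called a recurrence. After an R1 resection, tumour may still be present on Day 0. If it grows, an investigator may reasonably record progression, because nothing has come back. The word used for local recurrence in Table 1 and the term offered as a reason for stopping nivolumab both favour that choice. If the recurrence item then stays at no, the failure is not a DFS event under Table 2 as written.

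The error runs in one direction: missed or delayed failures raise DFS. It also concentrates in R1 patients. That matters for two planned comparisons: R0 against R1, and patients like CheckMate 577 against those unlike it. R1 patients would fall in the unlike group if R0 is one of the key criteria used to form it. Section 4.1.1.4 says that similar outcomes in those two groups would support use of nivolumab in almost all patients. Under-counting failures in the unlike group pushes towards that finding.

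**Working it through.** **1. Is there a rule linking the two items?** I compared the Synopsis, Tables 1 to 3 and sections 4.1.1.2 and 4.1.2.

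- The DFS event is recurrence or death.
- Progression is recorded at all visits with its own date. The only survival outcome that names it is PFS2, which starts at subsequent treatment.
- No passage says whether progression without a recorded recurrence is a DFS event.

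**2. When is an event lost?** Only if a site records progression and also leaves recurrence at no. The items are not mutually exclusive, so this depends on how each site codes, across more than 12 German and about 28 US sites (section 3.2).

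**3. How large could the effect be?** The protocol gives no R1 share, no DFS for R1 patients and no miscoding rate, and it states no figure to reproduce. All inputs here are assumptions:

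- R1 share of the cohort r: 5% to 15%
- true 24-month DFS in R1 patients S: 20% to 30%
- share of R1 failures that are local only: one third to one half (distant spread is clearly recurrence under Table 1)
- share of those local failures entered as progression only: 20% to 50%

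The fraction of R1 failures lost is f = local share × miscoded share. It runs from 1/3 × 0.20 = 0.067 to 1/2 × 0.50 = 0.25. If lost failures are treated as censored and hazards are proportional, apparent R1 DFS = S^(1−f). The overall shift = r × (apparent − true).

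| S | f | Apparent R1 DFS | Shift in R1 (points) | Overall shift, r = 5% | Overall shift, r = 15% |
|---|---|---|---|---|---|
| 0.20 | 0.067 | 0.223 | 2.3 | 0.1 | 0.3 |
| 0.20 | 0.167 | 0.262 | 6.2 | 0.3 | 0.9 |
| 0.20 | 0.25 | 0.299 | 9.9 | 0.5 | 1.5 |
| 0.30 | 0.067 | 0.325 | 2.5 | 0.1 | 0.4 |
| 0.30 | 0.167 | 0.367 | 6.7 | 0.3 | 1.0 |
| 0.30 | 0.25 | 0.405 | 10.5 | 0.5 | 1.6 |

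These figures give no credit for a later death that still counts as an event, which would make them smaller.

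**4. A second model as an outer bound.** This simulation uses exponential DFS with an R0 median of 22.4 months (the CheckMate 577 nivolumab median in section 1.1) and an R1 median of 11.0 to 22.4 months. It assumes 85% of first events are non-fatal. A miscoded failure becomes an event at death, with a median delay of 10 months. Here any non-fatal R1 failure can be miscoded, including distant ones, and the miscoded share runs from 25% to 100%. Overall 24-month DFS rises by:

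- 0.2 to 1.3 points at an R1 share of 5%
- 0.5 to 2.7 points at 10%
- 1.0 to 5.2 points at 20%

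The upper ends require every non-fatal R1 failure to be miscoded. With half miscoded, the rise is about 0.5 to 0.6, 1.0 to 1.3 and 1.9 to 2.6 points respectively.

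**5. Against the planned precision.** Section 4.2 plans for 7 points around a 24-month DFS of 40%. The overall shift in step 3 is at most 1.6 points, under a quarter of that (1.6 / 7 = 0.23).

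**The case against.** The strongest reply is that Table 1 already settles the matter. Its general definition of recurrence is broad and left to the investigator, so regrowth after an R1 resection can be entered there. The progression item has its own purpose in PFS2, and a site may complete both items. The reasons for stopping nivolumab do not feed DFS and include an open category. Section 5.1 acknowledges that both outcomes are prone to measurement error and promises clear definitions to sites. Most of this stands. It turns a certain loss of events into a possible one, but it does not supply the missing rule: two overlapping dated items remain, and only one is named in the primary endpoint.

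A reader might infer more than the protocol supports:

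- *That regrowth in R1 patients is excluded from DFS.* The general definition of recurrence does not exclude it.
- *That a later death can never restore a missed failure*, because assessment is before subsequent therapy. Table 2 states no censoring rule, and section 4.1.1 leaves censoring to the SAP. A death without subsequent therapy still counts.
- *That the effect reaches 25 points in R1 and 3.7 points overall.* This follows if half of all R1 failures are lost: 0.20^0.5 = 0.447, and 0.15 × 24.7 = 3.7. That fraction would have to include deaths and distant metastases, which Tables 1 and 2 plainly count.
- *That the DFS wording was copied from CheckMate 577.* It is nearly identical, but the protocol does not state its origin.

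**Conclusion.** The point holds as an unresolved boundary in the primary event definition. A failure recorded only as progression is not a DFS event under Table 2, and the study enrols patients in whom such recording is plausible. Whether events will actually be lost cannot be known from the protocol.

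Under the assumptions in step 3 of the working, the overstatement of overall 24-month DFS is about 0 to 2 points, so the primary estimate is not seriously threatened. Within R1 it could reach about 10 points, enough to blur the R0 against R1 comparison. The subgroup unlike CheckMate 577 would share the bias in proportion to its R1 content. The correction is worth making because the bias has one direction, is not reflected in the confidence interval, and costs little to remove.

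**What to change.** - In Table 2, define the DFS event as the earliest of investigator-recorded recurrence, investigator-recorded disease progression before subsequent anti-cancer therapy, or death from any cause. Apply the same rule to DFS rates, and bring the Synopsis wording into line.
- In Table 3, change the label among the reasons for stopping nivolumab to recurrence/progression, so that the form does not steer sites to one term. This changes a data label only.
- Leave time to recurrence as it is. It is a separate outcome, and adding progression would change its meaning.
- No new R0-only analysis is needed. The planned R0 subgroup, with median DFS by subgroup under section 4.1.3.1 where data allow, already serves that purpose.

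**Cost.** A few lines in the protocol, the matching lines in the SAP and one label on the case report form. Both items and their dates are already collected. DFS may come out slightly lower, and some DFS events may have no recurrence date, so DFS and time to recurrence will not always share a date.

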Physicians will be asked to enroll eligible patients consecutively until the total expected study sample size is reached or the end of the enrollment period (whichever occurs first). The enrollment period is anticipated to last approximately 18 months. The follow-up time will vary between patients due to the nature of the study with ongoing enrollment; patients will be followed for up to 42 months for the first patient in and up to 24 months for the last patient in. Patients will be followed until the end of study period, death, lost to follow-up, or withdrawal, whichever comes first. Patients will be censored at last record or assessment for those lost to follow-up.

Assessment schedules will be performed according to routine local clinical practice. Data collection and data entry by sites will start at Day 0 (baseline, i.e., the day of nivolumab initiation), and at the following months with a time window of +/- 15 days: months 3, 6, 9, 12, 18, 24, 30, 36, and 42 counted relative to treatment initiation (two and 3.5 years after nivolumab initiation for the first and last patient in, respectively). As this is a non-interventional study, no visits or measurements will be made mandatory by the protocol, and data collection at these prespecified timepoints will only take place if the patient visits the site as per standard of care. Investigators or qualified research staff should collect data from the visit nearest to the time point.

Sites will receive fees to compensate for the time spent for data collection and entry into eCRFs. Since the study is intended to reflect usual clinical practice, physicians will not be required to perform any mandatory patient assessments or laboratory tests that they would not ordinarily do in treating their patients. This protocol requires that sites submit all relevant documentation to their respective institutional review board (IRB) or Ethics Committee (EC) and obtain approval or acknowledgment of notification, depending on the local requirements. Participating patients must provide written informed consent prior to study commencement, and they have the right to withdraw from the study at any time. This study will be conducted with support of a clinical research organization (CRO).

An overview of study design and data collection is shown in Figure 1.

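### The DMFS definition stops counting metastases and deaths once subsequent therapy starts, which drops events after a treated local or regional recurrence and does not match the DMFS-rates row

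*Protocol*

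**What the plan says.** Protocol section 3.5.1.1, Table 2, starts DMFS at nivolumab initiation and ends it at the "date of appearance of distant metastasis or death from any causes, whichever occurs first, as assessed by the investigator prior to subsequent anti-cancer therapy". The DFS row closes with the same restriction, but its event is "the first date of recurrence (local, regional, or distant from the primary resected site) or death from any causes".

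Table 1 defines three types of recurrence. "Local recurrence is defined as a cancer that after treatment reappears at the primary site"; regional recurrence is in nearby nodes or tissue; metastatic recurrence is in distant organs or tissue. Only the last is a DMFS event.

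The DMFS-rates row of Table 2 gives "the probability that a patient is alive and presents no signs of metastasis at specific time points", with no mention of therapy. The OS row counts death from any cause, also without reference to therapy.

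Section 4.1.3.1 plans the DMFS median and rates together by Kaplan-Meier. The one general censoring rule is in section 3.1: "Patients will be censored at last record or assessment for those lost to follow-up". Starting another therapy does not end follow-up: "Patients will be followed until the end of study period, death, lost to follow-up, or withdrawal, whichever comes first".

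**The concern.** The clause fits DFS. A patient with a local recurrence has already had the DFS event, so therapy given for that recurrence removes nothing. In DMFS the same patient is still event-free when therapy starts, and from then on a metastasis or death falls outside the definition.

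The patients affected are mainly those whose disease has returned, a group whose risk is plausibly higher than that of patients without recurrence. If they are censored, Kaplan-Meier treats them as having the same future risk as those who remain. If they are kept event-free, real events are counted as non-events. Either way a secondary effectiveness outcome may look better than it is. Median and rates taken from one curve would also not answer the question that the rates row asks.

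**Working it through.** **Setting the rows side by side.** Take a hypothetical patient with a local recurrence at month 10, therapy for it from month 11, and death at month 20.

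| Table 2 row | Result |
|---|---|
| DFS | event at month 10 |
| OS | event at month 20 |
| DMFS | death follows subsequent therapy, so it is not counted |
| DMFS rate at month 24 | patient is not alive, so does not meet the rate definition |

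This mismatch needs no numerical assumption.

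**Size.** The protocol states no DMFS figure, so there is none to reproduce. The only event rate it gives is the 40% DFS rate at two years (section 4.2). Assumed, not in the protocol: constant hazards; a share p of first DFS events that are local or regional; and a median time from there to metastasis or death, which sets the hazard h.

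- First-event hazard: λ = −ln(0.40)/24 = 0.0382 per month.
- All events counted: S(t) = e^(−λt) + [pλ/(h − λ)] × (e^(−λt) − e^(−ht)).
- Censored at immediate therapy: Kaplan-Meier estimates e^(−(1−p)λt).
- Kept event-free from immediate therapy: e^(−λt) + p(1 − e^(−λt)).

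Central case, p = 0.30 and median 12 months (h = ln 2/12 = 0.0578), at t = 24:

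- All events counted: 0.40 + [0.01145/0.01958] × (0.40 − 0.25) = 0.40 + 0.585 × 0.15 = 48.8%.
- Censored: 0.40^0.7 = 52.7%, or +3.9 points.
- Kept event-free: 0.40 + 0.30 × 0.60 = 58.0%, or +9.2 points.

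With therapy starting one month after recurrence (simulation), the censored figure is 52.2% against 48.7%, or +3.5 points. Kept event-free it is 57.0%, or +8.3 points.

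Overstatement of 24-month DMFS under censoring, all patients treated one month after recurrence (simulation, error about 0.1 point):

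| Local/regional share | median 6 months | 12 months | 18 months |
|---|---|---|---|
| 20% | +4.1 | +2.0 | +0.6 |
| 30% | +6.5 | +3.5 | +1.5 |
| 40% | +9.2 | +5.3 | +2.9 |

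**Sensitivity to the assumptions.**

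- With 70% treated after a mean of 1.5 months, the central figure falls to +2.2 and the maximum to +5.7.
- Censoring bias is zero when h = (1 − p)λ. For p = 0.30 that is a median of ln 2/(0.70 × 0.0382) ≈ 26 months. At a 24-month median the bias runs from about −0.1 (20% share) to about +1 (40% share). At longer medians it can be slightly negative.
- The event-free reading does not cancel in this way. At a 25% share, a 24-month median and immediate therapy, it gives 0.40 + 0.25 × 0.60 = 55.0% against 50.3%.

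**The case against.** Censoring is not written anywhere in the DMFS row. The general rule covers only patients lost to follow-up, and section 4.1.1 leaves censoring methods to the SAP. That is right as far as it goes: a reader may infer that these patients are censored, but the protocol does not say so. It does fix which events count. An SAP that counted later events would depart from the definition, and one that followed it would carry the restriction forward.

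The DFS-rates row also omits the clause, so both rates rows can be read as shorthand for the time-point estimate of the outcome above. This tempers any claim of outright contradiction. For DFS, however, the omission changes little, while for DMFS it changes which deaths and metastases are included.

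The size, and for censoring the sign, depend on a post-recurrence hazard that the protocol does not give and on how many patients are treated. This stands, so the figures are illustrative only.

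The study is descriptive, DMFS is secondary, and OS and post-recurrence survival count all deaths. This also stands, and it limits the consequence.

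A reader might go further and link the clause to Table 3, where "If nivolumab is restarted after 3 missed infusions, it should be considered as a new line of therapy (LOT"), and conclude that a recurrence-free patient who restarts nivolumab leaves the DFS and DMFS risk sets. The protocol nowhere equates a new line of therapy with subsequent anti-cancer therapy, nor says that such patients are censored. That is a separate ambiguity and no part of this point.

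**Conclusion.** The point holds as a defect of definition. As written, DMFS excludes metastases and deaths after therapy for a local or regional recurrence, does not match the DMFS-rates row, and omits deaths that OS counts.

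Under the stated assumptions, censoring would overstate 24-month DMFS by about 0.6 to 9 points, central +3.5 if all are treated and about +2 if 70% are. It is near zero if the post-recurrence median is about 24 months. Keeping patients event-free would overstate it more. For scale, the protocol's target precision for the DFS rate is 7 points.

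The documents do not support saying that DMFS is certainly too high by a given amount, that risk is known to peak after local or regional recurrence, or that DMFS cannot be read beside OS. The primary DFS analysis is not affected by this mechanism. The change should be made, but it is not critical to the study's main result.

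**What to change.** In the DMFS row of Table 2, delete the restriction to the period before subsequent anti-cancer therapy. Define the event as the first distant metastasis or death from any cause, whatever therapy comes between. Word the DMFS-rates row as the time-point estimate of that same outcome; it currently opens by calling the quantity DFS rates. Keep the therapy-restricted version as a named sensitivity analysis, and state there whether patients are censored at the start of therapy.

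The cost is a wording change and one extra table. No new data are needed: follow-up continues after subsequent therapy, and recurrence, metastasis and death are scheduled for collection at all visits (Tables 3 and 4). The one small downside is that DMFS may look slightly less favourable.
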